**Table 7 Adverse Events of Special Interest**

AESI	Programmatical Derivation
TP-GDO-WW-016-03 Effective Date: 26 Aug 15 Related to: SOP-GDO-WW-019	CONFIDENTIAL Project Document Version No. 2.0 Project Document Effective Date: Date of last signature Page 56 of 80

Serious infections, including serious respiratory infections.	SAEs, Filter on infections SOC
Opportunistic infections including TB reactivation	Opportunistic infections will be adjudicated by the SRT, using the preferred terms list given in Appendix A . Final adjudication conducted by SRT.
Neutropenia	Based on Grade 3 or 4 absolute neutrophil count
PAP (Pulmonary alveolar proteinosis)	If identified then list all AEs for those subjects.
Hypersensitivity reactions, including anaphylaxis	Hypersensitivity reactions will be adjudicated by the SRT, using AE data and data from hypersensitivity reactions eCRF page. Final adjudication conducted by SRT.
Injection site reactions	Using data from Injection site reactions eCRF page

AEs with missing intensity will be considered severe. AEs with missing relationship to study medication will be considered as related both to GSK3196165/Placebo and to MTX.

Where dates are missing or partially missing, adverse events will be assumed to be treatment-emergent, unless there is clear evidence (through partial dates as described in section 4.5) to suggest that the adverse event started prior to the first dose of study treatment or more than 12 weeks after the last dose of study treatment.

Adverse Events will be summarised by system organ class (SOC) and preferred term (PT). Summaries will provide the number of subjects reporting at least one AE and the total number of events reported.

The following summaries of AEs will be provided by actual treatment group at the time of the AE:

- Overall summary of AEs, including number and percentages of subjects with
  - Any AE
  - Serious AE
  - Discontinuation due to AE
  - Drug-related AE
  - AE leading to death
- Overall summary of Adverse Events
- Number and percentage of subjects reporting an Adverse Events
- Most common AEs (reported by >5% of the subjects in total)
- Plot of Most Common Adverse Events and Relative Risk
- Number and percentage of subjects reporting an Adverse Events by maximum intensity
- Number and percentage of subjects reporting an adverse events by relationship to study treatment
- Number and percentage of subjects reporting an adverse events of special interest

- Number and percentage of subjects that withdraw from study or discontinue study treatment as result of an adverse event
- Number and percentage of subjects with adverse events during the initial treatment period (up to Week 14 visit)
- Number and percentage of subject reporting an adverse event by study period at the time of the first onset of the adverse events
- Exposure-adjusted (patient years) adverse events by treatment group, where the total number of subjects for each column includes all subjects who took the dose at least once during the study. The exposure-adjusted rate divides the total number of AEs attributed to each dose by duration of exposure (in years) to that dose. The duration for subjects who complete the study on their randomised dose is (date of last dose – date of first dose + 1). For subjects who escape, duration is based on treatment periods defined in Section 4.2.

Exposure adjusted incidence rates are calculated as  $X/T*100$  with

- X being the number of occurrences of the relevant AE for subjects while being in the corresponding treatment group
- T being the cumulative duration of exposure (in years) for subjects in the corresponding treatment group

Adverse event summaries will be ordered by decreasing frequency for SOC, and PT within SOC, summed up for all subjects and then alphabetically for SOC, and PT within SOC.

A by-subject listing of all adverse events will be provided as well as a by-subject listing of all AEs leading to withdrawal from study. These listings will be presented by actual treatment group and will include: center, subject identifier, age, sex, race, weight, adverse event (SOC, PT, and verbatim term), date of onset, date of resolution, duration, intensity, action taken, outcome, relationship to study medication, action taken with study medication, other action taken and whether the AE is treatment-emergent, serious and an AE of interest.

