**aEscape at W12:**

**Placebo, 22.5 mg, 45 mg, 90 mg or 135 mg.** Subjects that fail to achieve EULAR good or moderate response at W12, escalate to 180 mg (or the highest remaining dose) for remainder of study from W14

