### **4.10 Safety Evaluation**

All safety summaries and analyses will be based upon the ITT population by actual treatment group at the time of safety event or assessment. Actual treatment group is either the randomised treatment group or “Rescued Subjects” for subjects who got escalated. Only assessments that happen after the administration of the first dose of rescue treatment will be assigned to the treatment group of “Rescued Subjects”.

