#### 4.10.5 Respiratory Events

Numbers and percentages of subjects experiencing persistent cough, or persistent dyspnea or persistent DLCO decrease will be reported in a table by actual treatment group at the start time of the event.

Event	Definition
Persistent cough	Cough grade 2 or greater recorded for 3 consecutive weeks (15 or more days) on the eCRF page.
Persistent dyspnea	Borg Scale grade 3 or greater recorded for 3 consecutive weeks (15 or more days) on the eCRF page.
Persistent decrease of D LCO by >15%	Relative decrease of DLCOHCPP of $\geq 15\%$ compared to Baseline for 3 consecutive weeks (15 or more days)

These definitions are provided for guidance to identify potential cases. Final adjudication will be conducted by the SRT.

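### The relative-risk plot, the AESI table and the persistent respiratory-event table compare unequal observation times: every arm except 180 mg loses subjects to escape, and nothing in these outputs adjusts for it

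*SAP*

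**What the plan says.** SAP 4.10 states that safety summaries are "based upon the ITT population by actual treatment group at the time of safety event or assessment". It adds: "Only assessments that happen after the administration of the first dose of rescue treatment will be assigned to the treatment group of" rescued subjects, which is a separate column. SAP 3.1.1 and 3.1.3 set the escape rules. Week 12 EULAR non-responders on placebo or 22.5–135 mg "escalate to 180 mg (or the highest remaining dose) for remainder of study from W14". Those remaining on their original dose with DAS28 above 3.2 at Week 24 move at Week 26. The 180 mg arm has no escape. In all arms, Week 36 non-responders are withdrawn at Week 38.

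Three displays are affected:

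- SAP 4.10.2 and the DRC list in 4.10.11.1 both name a "Plot of Most Common Adverse Events and Relative Risk", with no period, denominator or comparator.
- SAP 4.10.2 lists "Number and percentage of subjects reporting an adverse events of special interest".
- SAP 4.10.5: "Numbers and percentages of subjects experiencing persistent cough", persistent dyspnea or persistent DLCO decrease "will be reported in a table by actual treatment group at the start time of the event".

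SAP 4.10.2 and 4.10.3 also plan exposure-adjusted AE and SAE rates. Section 4.10.2 adds an AE table for the initial period up to Week 14 and an AE table by study period. SAP 4.10.9 summarises cough grade and DLCO decrease above 15% by visit. The DRC list contains no exposure-adjusted or period-restricted event table.

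**The concern.** A percentage of subjects with an event can be compared between columns only if the columns were observed for similar lengths of time. Here a placebo subject who escapes at Week 14 contributes 14 weeks to the placebo column, and later events go to the rescued column. A 180 mg subject contributes up to 52 weeks, plus follow-up, because treatment-emergent AEs count to 12 weeks after the last dose (SAP 4.10.2). Equal hazards would therefore produce a crude relative risk above 1 for 180 mg.

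Opportunity for detection also differs. DLCO is measured every 3 months (Protocol 4.7.1), so a Week 14 escaper has one scheduled on-treatment test in the placebo column, against four by Week 52 for a 180 mg completer.

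Infections and pulmonary events are major secondary safety endpoints. The trial exists to choose doses for Phase 3, and the DRC can stop arms.

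**Working it through.** The documents give no person-time or relative-risk figure to reproduce, so the inputs were checked instead.

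**Inputs from the documents** (SAP 4.13)

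- Mean Week 12 change in DAS28(CRP): placebo −1.0, 135 mg −2.24, 180 mg −2.32; SD 1. The Emax formula with E0 = −1.0, Emax = −1.65 and ED50 of about 45 mg returns these means. For 180 mg: −1.0 − 1.65 × 180/225 = −2.32.
- Week 24 remission: 3% placebo, 33% active. Exact Fisher power with 35 per arm is 90.9%, against the stated approximately 90%.

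**Step 1: Week 12 escape on placebo, from the plan's figures alone.** Improvement of 0.6 or less is non-response at any DAS28, which gives a lower bound: Φ((0.6 − 1.0)/1) = Φ(−0.4) = 34.5%. If every subject with improvement of 1.2 or less were a non-responder, the upper bound is Φ(0.2) = 57.9%.

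**Step 2: full escape rules by simulation.** 400,000 subjects per setting, using the EULAR table, the DAS28 >3.2 rule and the Week 38 withdrawal. Assumptions not in the documents: baseline DAS28 mean 5.0–6.2, SD 0.9; between-visit correlation 0.5–0.85; Week 12 mean changes held afterwards; no other dropout.

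| | Placebo | 135 mg | 180 mg |
|---|---|---|---|
| Escape at Week 14 | 38–48% | 6–11% | none |
| Further escape at Week 26 | 37–46% | 31–61% | none |
| Mean weeks in column | 22–28 | 32–41 | about 51 |

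**Step 3: crude risk under equal hazards.** Risk in a column = mean of 1 − exp(−h·t/52), with the same constant h in every arm.

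Illustration at h = 0.2 per year. Risks over 14, 26 and 52 weeks are 5.24%, 9.52% and 18.13%. With placebo split 40% / 45% / 15% across those durations, placebo risk = 0.40 × 5.24 + 0.45 × 9.52 + 0.15 × 18.13 = 9.10%. A 180 mg arm observed for 52 weeks has 18.13%. The relative risk is 18.13/9.10 = 1.99 with no drug effect.

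Over the whole grid, with h from 0.1 to 0.6 per year and no follow-up time, the null relative risk versus placebo is:

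- 180 mg: about 1.7 to 2.3; counting the 12-week follow-up raises it to about 1.8 to 2.7.
- 135 mg: about 1.4 to 1.5.

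**Step 4: sensitivity.** Calibrating Week 24 escape to the 3% / 33% remission rates instead gives about 1.8 to 2.9 for 180 mg across event rates of 5 to 100 per 100 patient-years, with and without follow-up. With far lower placebo escape (20% at Week 14, then 40% of the rest), mean placebo time = 0.20 × 14 + 0.32 × 26 + 0.48 × 52 = 36.1 weeks, and the time ratio is still 52/36.1 = 1.44.

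**Step 5: the existing patient-year rate.** SAP 4.10.2 divides events by time from first to last dose for subjects who complete on their randomised dose, but counts events to 12 weeks beyond. For a 180 mg completer the last dose is Day 351 and the event window ends at Day 351 + 84 = 435. The ratio is 435/351 = 1.24, against about 1.0 for a placebo subject who escapes, whose exposure and events both end with the period. Reusing this rate unchanged would leave part of the bias in place.

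**The case against.** The strongest reply is that the final outputs already hold most of what is needed. AEs are summarised by SOC and preferred term. The exposure-adjusted rate is defined for the relevant AE, so it can be read term by term. A to-Week-14 table and a by-period table are planned. Serious infections are SAEs filtered on the infections SOC, so the exposure-adjusted SAE table largely covers them. Cough grade and DLCO decrease are shown by visit. All of this stands. A reader might infer that a real harm could not be told from longer observation anywhere in the final report; the documents do not support that.

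Nor do they support three other strong readings:

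- **That every higher dose looks riskier by construction.** Only 180 mg is exempt from escape by design. For 22.5–135 mg the bias arises only if the drug lowers escape rates, and it is smaller.
- **That the plot is stated to be crude and whole-study.** The SAP gives a title only. Whole-study subject percentages are the natural reading, and leaving this open is itself something to settle.
- **That the DRC sees nothing time-matched.** Its list has laboratory values by visit, including neutrophils. DRC shells are in a separate document, the protocol places Bayesian safety methods in the DRC Charter and guidance (Protocol 9.4.3), and the DRC may request individual data. Its first review, after about 5 weeks of treatment, precedes any escape.

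What the reply does not reach: several AESIs are not simple preferred-term counts. Opportunistic infections and hypersensitivity are adjudicated by the safety review team, neutropenia comes from laboratory grades, and injection site reactions come from a dedicated eCRF page. No time-adjusted AESI table is planned. The persistent respiratory events of 4.10.5 are also separate derivations without a rate. DRC reviews continue about every 12 weeks to study end, well after escape begins.

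**Conclusion.** The concern holds for the relative-risk plot (on its natural reading), AESIs other than serious infections, the persistent respiratory-event table and the DRC output list as written. With equal hazards, crude comparison of 180 mg with placebo would show a relative risk of about 1.7 to 2.3, more with follow-up counted. The direction follows from the design and the escape rules; the size depends on the baseline, correlation, held-change and constant-hazard assumptions listed in the working. Even much lower placebo escape leaves a time ratio of 1.44. For 135 mg the figure is about 1.4 to 1.5 and is conditional on efficacy.

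These are descriptive outputs with no formal safety test, and the primary endpoint is untouched. The risk is misreading dose-related safety, chiefly at 180 mg.

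**What to change.** 1. State the plot's period, denominator and comparator. Base it on Day 1 to before the Week 14 dose, when all arms have the same scheduled observation, or replace it with a patient-year rate-ratio plot.
2. Add exposure-adjusted AESI and persistent respiratory-event tables. Keep the whole-study crude tables, labelled as descriptive.
3. Add the exposure-adjusted and to-Week-14 AE and AESI tables to the DRC list, and align the separate DRC shells.
4. Match event and exposure windows in every rate: either count only events in on-treatment time, or add the 12-week follow-up to the denominator.
5. For DLCO and other late lung events, rely on the matched patient-year rate and the by-visit summaries. The pre-Week-14 window alone contains about one scheduled on-treatment DLCO test.

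The period definitions already exist in SAP 4.2, so the cost is SAP and shell wording, a corrected rate definition and a few more tables. The common-period comparison will contain fewer events and be less precise.

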#### **4.10.1 Extent of Exposure**

The extent of exposure to GSK3196165 will be evaluated by summarizing the number of injections, the amount of study medication received in mg and the duration of drug exposure in days. Exposure to GSK3196165 will be summarised by time period (Overall, Day 1 to <Week 14, Week 14 to <Week 26, Week 26 to <Week 38, and Week 38 to <Week 52).

Duration of drug exposure will be calculated as:

- date of the last injection during study – date of first injection during study + 1 day

Weekly MTX dose will be averaged across the entire study and within each time period for each subject.

MTX dose should be documented in mg, but in case ml is captured the following conversion should be used: 1ml is equivalent to 25mg.

A contingency table will be created for Week 12 and Week 24 showing the number of subjects that were escalated/not escalated correctly/falsely. For Week 36 a corresponding table will be created showing correct and false withdrawals due to lack of EULAR good/moderate response.

Overall Extent of exposure and extent of exposure by time period will also be presented in by-subject listings.

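### Exposure-adjusted AE and SAE rates: a completer's person-time stops at the last dose, but no stated rule stops the event count there

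*SAP*

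**What the plan says.** SAP 4.10.2 states: "The exposure-adjusted rate divides the total number of AEs attributed to each dose by duration of exposure (in years) to that dose". It computes the rate as 100·X/T, and SAP 4.10.3 repeats the construction for serious events.

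- **Numerator.** "X being the number of occurrences of the relevant AE for subjects while being in the corresponding treatment group".
- **T, completers.** The sentence beginning "The duration for subjects who complete the study on their randomised dose is (date of last dose" goes on to subtract the first-dose date and add one day.
- **T, escapers.** "For subjects who escape, duration is based on treatment periods defined in Section 4.2".
- **T, early withdrawals.** Neither section gives a rule.
- **Column size.** The number of subjects per column "includes all subjects who took the dose at least once during the study".

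Four other places bear on the reading:

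- SAP 4.10 defines the actual treatment group as the randomised group or Rescued Subjects: "Only assessments that happen after the administration of the first dose of rescue treatment will be assigned to the treatment group of" Rescued Subjects. This is the only exit from a group that it states.
- SAP 4.10.2 treats AEs as treatment-emergent until 12 weeks after the last dose. Protocol 7.4.4.1 collects AEs for equally long.
- SAP 4.10.1 ends its list of exposure periods with "Week 26 to <Week 38, and Week 38 to <Week 52". It computes duration as the last injection date minus "date of first injection during study + 1 day". It does not refer to the AE rates.
- SAP 4.2 lists five time periods, the fifth being the Safety Period from the Week 52 visit onward. The last dosing period closes the day before that visit. It closes 13 days after the last dose if the visit is missing or no end date can be found. SAP 4.2 also explains its period rule as a way of attributing AEs to the initial dose.

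**The concern.** A person-time rate can be interpreted only if events and time are taken over the same window. Here T has a stated end for completers and X does not. Protocol 5.6 defines a completed subject as one who has finished every phase including the follow-up visit. So the subjects whose T is cut at the last dose are the ones with 12 further weeks of AE collection.

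The tables exist to put arms with unequal time on dose on a common scale. The 180 mg arm has no escape, while the other five arms do (Protocol 6.4), so the mix of duration rules differs between arms by design. AE and SAE incidence is a major secondary safety endpoint in a study meant to select doses for Phase 3. A rate whose window depends on the programmer's reading is a weak basis for comparing doses.

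**Working it through.** **Schedule.** Protocol 4.6.1 doses on Days 1, 8, 15, 22 and 29, then every other week from Week 6 to Week 50 (Day 351). That is 5 + 23 = 28 doses, which agrees with SAP 4.8. The volumes there also reproduce, for example 28 × 1.2 mL = 33.6 mL and 28 × 0.15 mL = 4.2 mL. Other days from the Time and Events Table: Week 14 = 99, Week 26 = 183, Week 36 = 253, Week 52 = 365, Week 62 = 435 = 351 + 84.

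**Completer, T.** 351 − 1 + 1 = 351 days.

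**Completer, X, if follow-up events count.** X can run to Day 435, so 84 days of events have no person-time. Let r be the event rate after the last dose divided by the rate before it. The documents do not give r; the range 0 to 1 is an assumption. The ratio to the on-treatment rate is (351 + 84r)/351, so the overstatement is 84r/351:

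| r | Overstatement |
|---|---|
| 0 | 0% |
| 0.25 | 6% |
| 0.5 | 12% |
| 1 | 24% |

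**Completer, X, if events are attributed by SAP 4.2 period and the Safety Period is excluded** (as the list in SAP 4.10.1 suggests). X runs to Day 364 and T to Day 351. The uncovered window is 364 − 351 = 13 days, and 13/351 = 3.7%. That is the rate error if events are as frequent in those 13 days as before.

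**Escapers.** Randomised-dose time closes the day before the first rescue dose, and events change group at that dose, so this segment is matched. Only rescued time ends on a different day from completers' time. With the Safety Period excluded:

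- Week 14 rescue: Days 99–364 = 266 days, against 351 − 99 + 1 = 253 under the completers' rule. The difference is 13 days, 13/253 = 5.1%.
- Week 26 rescue: Days 183–364 = 182 days, against 351 − 183 + 1 = 169. The difference is 13 days, 13/169 = 7.7%.

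**Can the inflation differ by arm?** Suppose a share e of an arm escapes at Week 14, giving 98 matched days each. The rest complete, and rescued time is shown elsewhere. The randomised column's ratio is [(1 − e)(351 + 84r) + 98e] / [(1 − e)351 + 98e]. The shares are illustrative.

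- e = 0: 1.12 at r = 0.5 and 1.24 at r = 1.
- e = 0.6: 216.0/199.2 = 1.08 at r = 0.5 and 232.8/199.2 = 1.17 at r = 1.

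**Early withdrawals.** If the injection rule of SAP 4.10.1 is borrowed, a subject withdrawn for non-response at Week 36 (last dose Day 253) has ratio (253 + 84r)/253: 1.17 at r = 0.5 and 1.33 at r = 1.

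**The case against.** The best defence is that the language is tied to exposure. Events are attributed to a dose, time is exposure to that dose, and X is limited to time in the group. SAP 4.10.1 stops exposure before Week 52, SAP 4.2 sets the Safety Period apart, and SAP 4.10.2 does not define X as treatment-emergent events. An on-treatment reading is therefore possible. It stands as a reading, but no section states it. By period, it still leaves a completer's X 13 days beyond T. SAP 4.10.2 bounds another summary at the Week 14 visit and gives this one no bound.

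Other parts of the defence stand and limit the point:

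- Day 364 for escapers assumes that the Safety Period is excluded. SAP 4.10.2 speaks of treatment periods and SAP 4.2 of five time periods. If the Safety Period were included, escapers' T would run to Day 435.
- Windows of different length do not bias a rate when X and T match within each subject and the event rate is constant.
- A reader might infer that completers and escapers are mixed over mismatched windows in every randomised column. They are not, because the escapers' randomised segment is matched.
- A reader might see a contradiction between counting everyone who took a dose and the Rescued Subjects group. The former fixes the number of subjects per column. It does not allocate events or time, and SAP 4.10.2 presents its AE summaries by actual treatment group at the time of the event. The column for rescued time is unclear but not contradictory.
- SAP 4.10.2 also plans AEs in the initial treatment period and AEs by study period of first onset, and the listings give onset dates. A careful reader could largely separate follow-up events.

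**Conclusion.** The rule as written is faulty for completers: T has a stated end at the last dose, and nothing ends X there. If follow-up events are counted, a completer's rate is 0% to 24% above the on-treatment rate as r goes from 0 to 1. If events follow the SAP 4.2 dosing periods, the mismatch is 3.7%. If X is cut at the last dose, the completer's rate is sound, but the SAP does not say that it is. Rescued time ends 13 days later than completers' time if the Safety Period is excluded, and early withdrawals have no duration rule in SAP 4.10.2 or 4.10.3.

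Three stronger readings are not supported:

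- **A 24% overstatement whatever the follow-up rate.** This compares T to Day 351 with T to Day 435 (435/351 = 1.24). It takes as its target an at-risk rate that the SAP does not name.
- **A bias for or against 180 mg.** Inflation can differ by arm because that arm cannot escape. The net direction depends on escape, withdrawal and r, none of which the documents give.
- **An effect on study decisions.** The output list for each committee review (SAP 4.10.11.1) has no exposure-adjusted rate, and the stopping and arm-dropping criteria in SAP Table 4 are efficacy criteria.

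The effect is limited to descriptive AE and SAE tables. It is minor to moderate, and worth correcting because the correction is easy.

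**What to change.** In SAP 4.10.2 and 4.10.3, end X and T on the same day for completers, escapers and early withdrawals.

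- For the exposure rate that the SAP names, use the end of the SAP 4.2 dosing period for both: the day before the Week 52 visit, or 13 days after the last dose if that visit is missing or the subject withdraws.
- Close time in the randomised group the day before the first rescue dose. Start rescued time at that dose and end it by the same rule.
- Report events in the follow-up period separately.
- State whether rescued time appears under Rescued Subjects or in the 180 mg column.
- Say how this duration relates to the first-to-last-injection duration in SAP 4.10.1.

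The cost is a small rewording and one derived end date per subject. No new data are needed.
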